## 7.5. Preparation/Handling/Storage/Accountability

Investigators should consult the study drug information provided in the Pharmacy Manual.

## 7.6. Treatment Compliance

The study medication will be administered only at the investigational site by the authorized study site personnel. As a result, treatment compliance is ensured.

### 7.6.1. *Evaluable Patients*

#### 7.6.1.1 DLT-Evaluable Patients in Phase 1 Dose Escalation

Dose escalation refers to Cohort A1 to A5 or Cohort A1 to A6 (if Cohort A6 is opened).

A patient will be DLT evaluable if he or she experiences a DLT during the DLT observation period and has received at least one dose of study drug.

If a patient does not experience a DLT during the DLT observation period, he or she will be DLT evaluable if he or she receives all assigned doses of study drug(s) during the DLT observation period

Patients who receive all doses of study drug but discontinue from study treatment before the end of the DLT observation period will be considered DLT evaluable for the assessment of a dose level, provided it can be documented that the patient did or did not experience a DLT within the DLT observation period.

Patients who are not DLT evaluable may be replaced to ensure that enough patients complete the DLT observation period at each dose level, unless accrual to that cohort has stopped due to a DLT.

A patient may be deemed non-evaluable for assessment of a dose level in the event the patient experiences an AE which would meet DLT criteria, and furthermore has been determined through discussion between investigator and Lilly CRP/CRS to most likely be related to a concomitant medication or a prior line of immune therapy (in the case of irAEs) due to previously established linkage.

To ensure collection of adequate PK or biomarker data, patients who complete the DLT observation period but who do not have a valid PK or biomarker assay result may be replaced, upon consultation with the investigator(s) and the Lilly CRP/CRS, unless accrual to that cohort has stopped because of a DLT. Patients who are replaced for purposes of the PK or biomarker analysis are still considered DLT evaluable.

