### 7.2.2.2. Dose-Limiting Toxicity Determination

A DLT is defined as any of the events listed in [Table JZEA.8](#), if both the following criteria are met:

- the event occurs during the DLT observation period (Cycle 1, 42 days) for Cohort A1, (Cycle 1, 28 days) for Cohorts A2 to A5 (A2 to A6 if Cohort A6 is opened), (Cycle 1 and 2, 42 days) for Cohorts A7 and A8, and
- the event is clinically significant and definitely, probably, or possibly related to LY3434172, in the opinion of the investigator.

Patients in Cohorts A1 to A5/6, A7, and A8 who experience a DLT in Cycle 1 will be discontinued from study treatment.

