
 
Other Grade 3 or 4 laboratory value lasting <math>>14</math> days or requiring medical intervention
 
ALT or AST: 
 
<math>>8 \times</math> ULN, if the patient does not have HCC or liver metastasis
 
 
 
<math>\geq 2</math>-fold above the patient's baseline value that lasts <math>>7</math> days, if the patient has HCC or liver metastasis and had ALT or AST <math>>3.0 \times</math> ULN at baseline
 
<math>>3 \times</math> ULN with concomitant bilirubin <math>>2 \times</math> ULN, in the absence of cholestasis
 
Total bilirubin <math>>3 \times</math> ULN
 
<math>\geq</math>Grade 3 amylase or lipase that is associated with symptoms or clinical manifestations of pancreatitis
 

Other hematologic or nonhematologic toxicity

 
Grade 5 toxicity (i.e. death)
 
<math>\geq</math>Grade 3 electrolyte abnormality that lasts <math>>72</math> hours unless the patient has clinical symptoms, in which case all Grade 3+ electrolyte abnormality regardless of duration should count as a DLT.
 
Toxicity deemed by the investigator and the Lilly CRP/CRS to be dose limiting, such as: 
 
toxicity that is possibly related to study treatment and requires discontinuation of the patient from the study at any time during Cycle 1, or
 
persistent Grade <math>>2</math> toxicities causing a delay of <math>>14</math> days in initiating Cycle 2
 
Grade 3 vasculitis
 
 
 

Abbreviations: AE = adverse event; ALT = alanine transaminase; AST = aspartate transaminase; CRP = clinical research physician; CRS = clinical research scientist; HCC = hepatocellular carcinoma; irAE = immune-related adverse event; IV = intravenous; ULN = upper limit of normal.

Potential DLTs that are adverse events, which are reasonably anticipated AEs for concomitant medication should be reviewed by the treating investigator and Lilly CRP/CRS before final determination as a DLT. Review and discussion may include additional participating investigators. Such review may determine that confounding factors render the case to be not evaluable for the purposes of dose selection.

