#### **7.2.2.2.1. Events That Are Not Considered to Be DLTs**

**The following events will not be considered to be DLTs:**

- Toxicity that is clearly and directly related to the primary disease or to another etiology
- Grade 3 endocrine disorder (thyroid, pituitary, and/or adrenal insufficiency), if both the following criteria are met:
  - the disorder is manageable with or without systemic corticosteroid therapy and/or hormone replacement therapy, and
  - the patient is asymptomatic
- Grade 3 inflammatory reaction attributed to a local antitumor response (such as, inflammatory reaction in the lymph nodes or at sites of metastatic disease)
- Any grade vitiligo or alopecia
- First occurrence of Grade 3 infusion-related reaction (IRR) during infusion of LY3434172, if both of the following criteria are met:
  - the patient did not receive corticosteroid prophylaxis, and
  - the Grade 3 IRR resolves within 6 hours with appropriate clinical management
  - If symptoms reappear, the event would be considered a DLT.
  - If this first occurrence is anaphylaxis of any grade, the event would be considered a DLT.
- Grade 3 or 4 neutropenia meeting both of the following criteria are met:
  - is not associated with fever or systemic infection, and
  - improves by at least 1 grade within 7 days
- Grade 3 or 4 lymphopenia

It should be recognized that for patients who have received prior immune therapy, including checkpoint inhibitor therapy, there is the potential for delayed manifestation of serious irAEs such as colitis, hepatitis, pneumonitis, and endocrinopathies. Patients manifesting potential delayed irAEs should receive prompt evaluation and treatment.

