### **6.12.2. Dose-Limiting Toxicities and DLT-Equivalent Toxicities**

Definitions of DLTs and DLT-equivalent toxicities (DETs) are provided in Section 7.2.2.2 of Protocol JZEA.

Dose-limiting toxicities will be summarized and listed for the DLT-evaluable population (defined in Section 7.6.1 of Protocol JZEA), and DETs will be listed and summarized for the safety population.

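### The rule for setting aside DLT-type events overlaps with the protocol's own DLT definition, and no DLT count with those events put back is specified

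*Protocol*

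**What the plan says.** **DLT definition.** Under Protocol 7.2.2.2, an event listed in Table JZEA.8 is a DLT if it falls in the observation window and "the event is clinically significant and definitely, probably, or possibly related to LY3434172, in the opinion of the investigator".

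**Events that are not DLTs.** Protocol 7.2.2.2.1 sets a different bar for other causes: "Toxicity that is clearly and directly related to the primary disease or to another etiology".

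**Evaluability.** Protocol 7.6.1.1 first makes any patient evaluable who has had at least one dose and a DLT in the window. It later allows a patient to be deemed non-evaluable "in the event the patient experiences an AE which would meet DLT criteria", if the investigator and the sponsor's physician or scientist conclude that the event would "most likely be related to a concomitant medication or a prior line of immune therapy". The prior-therapy limb is confined to immune-related events, and the linkage must already be established. On replacement it says: "Patients who are not DLT evaluable may be replaced to ensure that enough patients complete the DLT observation period at each dose level". The one bar is that accrual to the cohort has stopped because of a DLT.

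**Second route.** The text under Table JZEA.8 provides for review of potential DLTs that are anticipated effects of concomitant medication: "Such review may determine that confounding factors render the case to be not evaluable for the purposes of dose selection".

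**SAP.** Section 6.12.2 states: "Dose-limiting toxicities will be summarized and listed for the DLT-evaluable population", and refers to Protocol 7.6.1 for the definition. SAP 6.2.1 gives its own definition: patients who completed the window, or who stopped treatment early with a documented DLT assessment. It contains no exclusion by attribution.

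**The concern.** Three thresholds govern one judgement: at least *possibly* due to study drug (a DLT), *clearly and directly* due to something else (not a DLT), and *most likely* due to something else (patient non-evaluable). The first and third overlap. An immune-related event can be most likely a late effect of an earlier checkpoint inhibitor and still possibly due to a PD-1/PD-L1 bispecific.

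The overlap is realistic. Inclusion criterion 1 admits patients with prior anti-PD-1 or anti-PD-L1 therapy. Protocol 7.2.2.2.1 warns of delayed immune-related events from such therapy. Protocol 7.4 expects the same kind of event from LY3434172, possibly soon after the first dose.

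The decision is taken after the event, in an open-label study, and only for patients who had an event. No matching attribution clause removes a fully dosed patient without one. DLTs are a primary endpoint and feed the mTPI-2 rule in cohorts that may contain three patients, so a single decision can matter.

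**Working it through.** **Inputs from the documents.** The target DLT rate is 30%, the equivalence interval is 25% to 35%, and the minimum cohort is three (Protocol 7.2.2.1). Appendix 8 gives 0/3 Escalate, 1/3 Stay, 2/3 De-escalate; 1/6 Escalate, 2/6 Stay, 3/6 De-escalate, 4/6 De-escalate with the dose barred (DU).

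**Reproducing the plan's rule.** I used mTPI-2 with intervals of width 0.10 built out from 25% to 35%. I assumed a Beta(1,1) prior and a 0.95 cut-off for DU, since the documents state neither. This returns every Appendix 8 cell for 1 to 7 patients, including the worked examples 1/3, 1/6, 2/3 and 5/7, and the 2/6 example in 7.2.2.1. The cells used below all lie in that range.

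**Effect of one decision, with no assumed share.** Set aside one patient with a DLT and replace with a patient who has none:

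| Counted under 7.2.2.2 | After replacement |
|---|---|
| 1/3 Stay | 0/3 Escalate |
| 2/3 De-escalate | 1/3 Stay |
| 2/6 Stay | 1/6 Escalate |
| 3/6 De-escalate | 2/6 Stay |
| 4/6 DU | 3/6 De-escalate |

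**Effect on the rate, with an assumed share.** Let p be the DLT rate under 7.2.2.2 and f the share of DLT patients set aside and replaced. Of all dosed patients, pf are removed and 1 − pf remain, of whom p(1 − f) have a DLT. The apparent rate is therefore p(1 − f)/(1 − pf), which is below p for every f > 0. The documents do not give f. I assume 10%, 25% and 50%.

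- p = 0.30: 0.27/0.97 = 27.8%; 0.225/0.925 = 24.3%; 0.15/0.85 = 17.6%.
- p = 0.40: 0.36/0.96 = 37.5%; 0.30/0.90 = 33.3%; 0.20/0.80 = 25.0%.

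Solving for f, a true 40% reaches an apparent rate t when f = (p − t)/[p(1 − t)]:

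- t = 35%, the top of the interval: 0.05/(0.40 × 0.65) = 19%.
- t = 30%, the target: 0.10/(0.40 × 0.70) = 36%.

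**Effect on escalation in a cohort of exactly three.** P(0/3) = (1 − apparent rate)³.

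| True rate | None removed | 25% removed | 50% removed |
|---|---|---|---|
| 30% | 0.700³ = 34% | 0.757³ = 43% | 0.824³ = 56% |
| 40% | 0.600³ = 22% | 0.667³ = 30% | 0.750³ = 42% |

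For a cohort of exactly six at a true 40%, P(0 or 1 DLT) goes from 23% to 35% and 53% under the same two shares.

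**SAP definitions side by side.** Take a patient with an excluded DLT-type event who completed the window, or who stopped early with a documented assessment. That patient is in the DLT-evaluable population under SAP 6.2.1, and out of it under SAP 6.12.2 through its reference to Protocol 7.6.1.

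**The case against.** **The clause is narrow.** It is permissive. For prior immune therapy it reaches only immune-related events, and it requires an established linkage and a joint discussion. Replacement is barred once accrual has stopped for a DLT. Inclusion criterion 1 already keeps out patients who had a Grade 3 or higher immune-related event, or any-grade pneumonitis, on prior immunotherapy. Many Table JZEA.8 events are not immune-related, so the prior-therapy route cannot reach them. All this stands and argues for the lower end of the assumed range.

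**The exclusion may be right.** If each removed event was truly not caused by LY3434172, the drug-caused rate is not understated, and counting every such event would overstate it. This stands. The calculation shows a shift against the protocol's own DLT label, not against true drug toxicity.

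**Non-events drop out too.** A reader might infer that only bad outcomes can leave the evaluable set. The documents do not support that for 7.6.1.1 as a whole: a patient without a DLT who misses assigned doses is also non-evaluable and replaceable, which pushes the rate up. The one-way effect belongs to the attribution clause alone.

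**The events are not hidden.** A reader might infer that the final report would conceal them. It would not: these patients stay in the safety population, and SAP 6.12.3 lists every adverse event with grade, relationship, seriousness and outcome. Protocol 10.3.1 even describes a DLT-equivalent count covering any study period, close to the missing second count. But the section on DLT-equivalent toxicities confines that term to events outside the DLT window, so an excluded in-window event has no assured place there.

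**Escalation is not mechanical.** Decisions are discussed and recorded in writing (7.2.2), an Escalate result can be overridden conservatively (7.2.2.1), and RP2D selection draws on all the data (7.2.2.3). That softens the consequence. It does not make the tabulated DLT count or the Appendix 8 action show what was set aside.

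**Conclusion.** The sections conflict and must be reconciled. Where the clause is applied to an event that is also possibly related to LY3434172, the DLT count is lower than the protocol's own definition gives, and a single use can change the Appendix 8 action at three or six patients. That conclusion needs no assumption about frequency.

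The size of any shift in the rate cannot be derived from the documents. The figures of 27.8%, 24.3% and 17.6% for a true 30%, and 37.5%, 33.3% and 25.0% for a true 40%, rest on assumed shares of 10%, 25% and 50%, on every removed patient being replaced, and on each removed event being a DLT under 7.2.2.2. The escalation probabilities also assume a fixed cohort size, which 7.2.2.1 does not impose.

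The stronger statement, that the primary endpoint is biased downward, is not supported. The clause may never be used, and where it is used the attribution may be correct. Nor is it settled that the SAP analyses a reduced set, because 6.2.1 and 6.12.2 disagree. The supported point is an outcome-dependent exclusion with overlapping criteria and no specified analysis to show its effect.

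**What to change.** 1. Reconcile Protocol 7.2.2.2 (including the text under Table JZEA.8), 7.2.2.2.1 and 7.6.1.1, so that an event both possibly related to study drug and more likely due to something else has one stated status. Which threshold should govern is for the sponsor and investigators to decide.
2. Give the DLT-evaluable population one definition across SAP 6.2.1, SAP 6.12.2 and Protocol 7.6.1.
3. In SAP 6.12.2, report DLTs per dose level twice: as decided, and with every attribution-excluded DLT-type event counted as a DLT and its patient kept in the denominator. List each such exclusion with its reason.
4. At each cohort review, record the Appendix 8 action under both counts.

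The cost is one extra table, a short listing and a line in the review template. Clinical judgement on attribution is untouched, and if the clause is never used the two counts agree. The downside is that the DLT rate may look less favourable, and that the second count will include some events the drug did not cause. It should therefore be labelled as a sensitivity count.

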## 7.7. Concomitant Therapy

[Appendix 5](#) describes medications, treatments, and drug classes that are restricted or prohibited for use during the study treatment period, including exceptions and conditions. There are no prohibited therapies during the post discontinuation follow-up period. Patients who, in the opinion of the investigator, require the use of any of the prohibited treatments for clinical

management should be discontinued from the trial. Patients may receive other supportive therapy that the investigator deems to be medically necessary.

In general, medications or live vaccinations specifically prohibited in the exclusion criteria are not allowed during the ongoing trial except with approval from Lilly CRP/CRS.

No other chemotherapy, systemic radiotherapy, immunotherapy, cancer-related hormone therapy, experimental drugs, herbal supplements intended to treat cancer will be permitted while the patients are on this study.

Palliative radiation therapy to small areas of painful metastases that cannot be adequately managed with systemic or local analgesics is permitted after discussion with and agreement of the Lilly CRP/CRS.

In addition, any disease progression requiring other forms of specific antitumor therapy will also necessitate early discontinuation from study treatment. Appropriate documentation for all forms of premedication, supportive care, and concomitant medications must be captured on the eCRF. Replacement hormonal therapy initiated before study entry will be allowed.

Patients should receive full supportive care. The use of granulocyte-colony stimulating factor (G-CSF) is permitted at the discretion of the investigator based on ASCO (Smith et al. 2015) and European Society for Medical Oncology (Crawford et al. 2010) guidelines.

If clinically indicated at any time during the study, erythropoietin and packed red blood cell transfusions may be used according to ASCO guidelines (Rizzo et al. 2008). Prophylactic antibiotic treatment should be consistent with ASCO guidelines (Flowers et al. 2013).

All concomitant medications should be recorded throughout the patient's participation in the study.

## **7.8. Treatment after the End of Study**

The end of study definition is defined in Section 5.3. Investigators will continue to follow the schedule of activities provided in Section 2 until notified by Lilly that end of study has occurred.

### **7.8.1. Treatment after Study Completion**

Study completion will occur following the final analysis of primary and secondary objectives, as determined by Lilly. Investigators will continue to follow Schedule of Activities (Section 2) for all patients until notified by Lilly that study completion has occurred.

#### **7.8.1.1. Continued Access**

[figure not shown]
Patients who are still on study treatment at the time of study completion may continue to receive study treatment if they are experiencing clinical benefit and no undue risks.

The continued access period will apply to this study only if at least one patient is still on study treatment when study completion occurs. Lilly will notify investigators when the continued access period begins.

Lilly may allow patients to enroll in a “rollover” protocol to provide long-term continued access for patients enrolled in this study.

Patients who are in short-term follow-up when the continued access period begins will continue in short-term follow-up until the 90-day short-term follow-up visit is completed. Long-term follow-up does not apply.

Patients who are in long-term follow-up when the continued access period begins will be discontinued from long-term follow-up.

a Lilly will notify sites when the continued access period begins and ends.

b Final analysis of overall survival. Lilly will notify sites when study completion occurs.

c End of study occurs at the last visit or last scheduled procedure for the last patient.

**Figure JZEA.2. Continued access diagram.**

## 8. Discontinuation Criteria

The reasons for treatment and study discontinuation and the dates of discontinuation will be collected for all patients.

Patients who discontinue during the study treatment period, whether or not they received study treatment, will have follow-up procedures performed as shown in the Schedule of Activities (Section 2).

If a patient withdraws informed consent, he or she must not be contacted unless he or she has explicitly provided permission and consent. Lilly may continue to use previously collected medical research data prior to the withdrawal consistent with the original authorization.

### 8.1. Discontinuation from Study Treatment

Patients will be discontinued from study treatment in the following circumstances:

- the patient is enrolled in any other clinical study involving an investigational product or any other type of medical research judged not to be scientifically or medically compatible with this study.
- the patient becomes pregnant during the study
- the patient is significantly non-compliant with study procedures and/or treatment as described in Section 7.6
- The patient experiences a DLT (see Section 7.2.2.2) during Cycle 1, a DLT-ET (see Section 7.2.2.2.2), or other unacceptable toxicity
- the patient requires a dose delay of >28 days for Q2W schedule and >21 days for Q3W schedule, except as described in Section 7.4
- the patient, for any reason, requires treatment with another therapeutic agent that has been demonstrated to be effective for treatment of the study indication. Discontinuation from study treatment will occur prior to introduction of the new agent
- the investigator decides that the patient should be discontinued from study treatment, for reasons such as but not limited to confirmed disease progression (see Section 9.1.1).
- the patient requests to be discontinued from study treatment

Patients who are discontinued from study treatment will have follow-up procedures performed as shown in the Schedule of Activities (Section 2).

Discontinuation of study treatment may be considered for patients who meet all of the following criteria:

- have a confirmed complete response (CR), **and**
- have received study treatment for at least 24 weeks, **and**
- have received at least 2 cycles of study treatment beyond the date when the initial CR was declared.

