### 7.2.1. Selection and Timing of Doses

The doses will be administered at approximately the same times on each day. The actual time of all dose administrations will be recorded in the electronic case report form (eCRF).

A cycle is defined as an interval of 28 days (Q2W regimen) and 21 days (Q3W regimen) as shown in [Table JZEA.7](#). A delay of a cycle due to holiday, weekend, bad weather, or other unforeseen circumstances will be permitted for a maximum of 7 days and not counted as a protocol deviation. The reason for the delay should be documented on the eCRF.

The first study treatment will be administered within 7 days after the patient is assigned to a treatment cohort. There should be a minimum of 14 days between doses of study drug for all cohorts in Q2W schedule and 21 days between doses of study drug for the Q3W schedule. However, if there is a delay due to holiday, weekend, bad weather, or other unforeseen circumstances, a flexibility of  $\pm 3$  days is permitted.

A patient may continue to receive LY3434172 until he or she meets one or more of the specified reasons for discontinuation (see Section 8).

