#### **7.2.2.2 DLT-Equivalent Toxicities**

A DLT-equivalent toxicity (ET) is an AE that meets the DLT criteria as defined above and occurs in any cycle other than the DLT assessment period (28 days for Q2W schedule and 42 days for Q3W schedule). In addition to the DLT assessment period, available safety data beyond the DLT assessment period may also be taken into consideration prior to a decision to advance to the next dose level or the determination of the RP2D.

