### 7.4. Dose Modification

No dose modification is allowed during the DLT observation period (Cycle 1). See Section 8 for discontinuation criteria. See Section 7.6.1.1 for the definition of DLT-evaluable patients.

After the DLT observation period (Cycle 1), doses of the study drug may be delayed or discontinued to manage specific AEs or other toxicities. Dose reductions are not permitted. All dose modifications should be documented, including the approach taken and a clear rationale for the need for modification.

The investigator must assess whether the toxicity is at least possibly due to study treatment and apply the dose-modification guidelines. Investigators are encouraged to consult Lilly for additional guidance.

If a patient requires a dose delay, study treatment should be resumed within 1 cycle, if possible and appropriate. If study treatment cannot be resumed within 1 cycle, every effort should be made to restart on the first day of the next cycle. In rare circumstances, a delay of >28 days may be permitted before permanent treatment discontinuation, as long as the patient demonstrates clinical benefit, does not have objective progression, and is recovering from the toxicity. Such circumstances must be discussed with the Lilly CRP/CRS.

Adverse events of immune-related etiology are expected because of the study drug's mechanism of action and may occur shortly after the first dose or several months after the last dose. Study treatment must be withheld if the patient experiences a drug-related toxicity or a severe or life-threatening AE. Dose reductions are not permitted.

A 4-hour observation period following the end of LY3434172 administration will occur in Cycles 1 to 3. During observation period, patients treated with LY3434172 should be closely monitored for signs and symptoms indicative of an infusion-related reaction by medical staff from the start of the infusion, in an area where emergency medical resuscitation equipment and other agents (epinephrine, prednisolone, or equivalents, etc.) are available. LY3434172 infusion-related reactions will be defined according to the Common Terminology Criteria for Adverse Events (CTCAE), version 5.0 definition of IRRs.

Table JZEA.9 presents instructions for management of infusion-related reactions associated with LY3434172.

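### In the Q3W cohorts (A7, A8) a DLT on days 22–42 triggers neither of the protocol's DLT-specific mandatory stops

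*Protocol*

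**What the plan says.** - **Window and cycle length.** Protocol Section 7.2.2.2 sets the DLT observation period as "Cycle 1 and 2, 42 days) for Cohorts A7 and A8". Section 7.2.1 says "A cycle is defined as an interval of 28 days (Q2W regimen) and 21 days (Q3W regimen".
- **Stop for a DLT.** Section 7.2.2.2 states "Patients in Cohorts A1 to A5/6, A7, and A8 who experience a DLT in Cycle 1 will be discontinued from study treatment". Section 8.1 lists, among the circumstances that require discontinuation, "The patient experiences a DLT (see Section 7.2.2.2) during Cycle 1, a DLT-ET (see Section 7.2.2.2.2), or other unacceptable toxicity".
- **Stop for a DLT-ET.** Section 7.2.2.2.2, the definition that Section 8.1 cites, describes an event that meets the DLT criteria and "occurs in any cycle other than the DLT assessment period (28 days for Q2W schedule and 42 days for Q3W schedule".
- **Dose changes.** Section 7.4 says "No dose modification is allowed during the DLT observation period (Cycle 1". After that, doses may be delayed or stopped but never reduced. Drug-related toxicity, and severe or life-threatening events, require dosing to be withheld.
- **Delay limit.** Section 8.1 also stops treatment if "the patient requires a dose delay of >28 days for Q2W schedule and >21 days for Q3W schedule, except as described in Section 7.4". The exception in Section 7.4 reads "In rare circumstances, a delay of >28 days may be permitted before permanent treatment discontinuation". It applies only if the patient is benefiting, has not progressed and is recovering, and it must be discussed with the sponsor.

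**The concern.** The two DLT-specific stops should meet at the end of the DLT window, so that every event meeting the DLT criteria ends treatment whenever it occurs. In the Q2W cohorts they do. In A7 and A8 the first stop ends with Cycle 1 and the second begins after Cycle 2, so all of Cycle 2 lies between them. The documents give no reason for treating a mid-window DLT more leniently than an earlier or later one. The likely cause is Q2W shorthand carried over: Section 7.4 also equates the DLT period with Cycle 1, whereas the DLT-ET definition and the delay limit were adapted to Q3W.

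What is at stake is the safety of individual patients in a first-in-human study. Because dose reduction is not allowed, a patient re-dosed after a Cycle 2 DLT receives the dose level that caused it.

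**Working it through.** **1. The plan's own figure.** Two Q3W cycles of 21 days give 2 × 21 = 42 days, as Section 7.2.2.2 states.

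**2. Each study day against the two DLT-specific stops.**

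| Cohorts | Cycle | DLT window | Cycle 1 DLT stop | DLT-ET stop | Covered by neither |
|---|---|---|---|---|---|
| A7, A8 | 21 days | 42 days | days 1–21 | day 43 on | days 22–42: 42 − 22 + 1 = 21 days |
| A2–A6 | 28 days | 28 days | days 1–28 | day 29 on | none |
| A1 | 28 days | 42 days | days 1–28 | day 29 on | none |

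A1 has no gap because the DLT-ET definition uses 28 days for every Q2W cohort, so its days 29–42 are covered there.

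**3. Which Cycle 2 DLTs are stopped by another explicit rule.** I set the DLT list (Table JZEA.8) beside Tables JZEA.9 and JZEA.10.

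- Stopped outright: for example Grade ≥3 pneumonitis, ALT or AST above 5 × ULN, bilirubin above 3 × ULN, creatinine above 6 × ULN, Grade 3–4 non-thyroid endocrine events, cardiac events and anaphylaxis.
- Stopped conditionally: Grade 3 colitis. Treatment ends if it lasts more than 3 days despite steroids or if Grade 3 persists; otherwise it may resume at Grade ≤1.
- No discontinuation row: Grade 4 thrombocytopenia, febrile neutropenia, transfused Grade ≥3 anemia, non-endocrine Grade ≥3 fatigue beyond 7 days, hypertension, electrolyte abnormalities, and laboratory DLTs other than hepatic or creatinine values with a stop row.

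**4. Does the delay limit catch the last group?** The third dose is due on day 43 (Appendix 4, C3D1). Let d be the onset day (22 to 42) and r the days to recovery. I assume on-schedule dosing, delay counted from day 43, restart on recovery, and no use of visit windows. The recovery times are illustrative, since the documents give none.

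Without a steroid taper, delay = max(0, d + r − 43), and the limit is passed only if d + r > 64.

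| r (days) | Onset days needing no delay | Longest delay (d = 42) | Onset days caught |
|---|---|---|---|
| 8 | 14 of 21 (d ≤ 35) | 7 days | 0 of 21 |
| 15 | 7 of 21 (d ≤ 28) | 14 days | 0 of 21 |
| 22 | 0 of 21 | 21 days | 0 of 21 |
| 23 | 0 of 21 | 22 days | 1 of 21 |

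The case r = 8 is the shortest that fits a fatigue DLT, which must last more than 7 days.

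**5. With a taper.** Section 7.4 asks for a one-month taper from Grade ≤1, completed before restart. Taking 30 days, delay = d + r + 30 − 43 = d + r − 13, which exceeds 21 when d + r > 34. Onset days that still allow restart within the limit:

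- r = 3: d ≤ 31, 10 of 21 (12 with a 28-day taper, 9 with a 31-day taper)
- r = 7: d ≤ 27, 6 of 21 (8 and 5)
- r ≥ 13: 0 of 21 with a 30-day taper

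The taper closes most of the gap for steroid-treated events, though not for early onset with fast recovery. Without a taper the limit closes almost none of it.

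**The case against.** The strongest reply is that the same Section 8.1 bullet ends with a mandatory limb for other unacceptable toxicity. A DLT is by definition clinically significant and at least possibly drug-related, so an ordinary reader would apply that limb on days 22–42. Several other controls point the same way:

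- the investigator may stop treatment;
- Section 5.1.1 provides for sponsor–investigator safety reviews during and at the end of each cohort's DLT period, which for A7/A8 ends the day before the nominal third dose;
- Section 7.4 has possible immune-related events managed under ASCO guidance, and requires consultation with the sponsor for immune-related events missing from Table JZEA.10. A cytopenia judged immune-related would come under this.

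All of this stands as mitigation. But the unacceptable-toxicity limb is undefined, the other controls rest on judgment or govern the cohort, and none requires an individual patient to stop. For DLTs in Cycle 1 and for DLT-ETs the protocol chose a fixed rule instead.

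Section 10.3.1 also describes DLT-equivalent events more broadly, as DLT-type events in any period of the study. That is a tabulation rule. Section 8.1 points to Section 7.2.2.2.2, so the narrower definition governs discontinuation.

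A reader might infer that six patients are certain to come under the wording. The documents do not guarantee this. Section 5.2 plans at least three per cohort (2 × 3 = 6), but Section 7.2.2.1 excepts de-escalation and Section 5.1 says only that Q3W dosing could be started.

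**Conclusion.** The gap is real and the wording should be changed. In A7 and A8, a DLT on days 22–42 meets neither DLT-specific mandatory stop. The practical remainder is mainly DLTs with no discontinuation row and no long taper that are not managed as immune-related. For these, under the assumptions above, recovery within 22 days never breaches the delay limit.

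Three stronger readings are not supported. First, the protocol does not direct re-dosing after a Cycle 2 DLT: re-dosing is permitted, and only after withholding. Second, 21 of 42 days does not mean that half the DLT risk is uncovered; the documents give no event rate, and the number of patients affected is unknown. Third, the discontinuation rule does not distort dose escalation, because mTPI-2 decisions rest on DLTs as defined in Section 7.2.2.2 and not on whether the patient stops.

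DLT reporting is a separate matter. Section 10.3.1 summarizes DLTs during Cycle 1, and the DLT-evaluable population in SAP 6.2.1 labels the window as Cycle 1. Read literally, that wording would leave Cycle 2 DLTs in A7/A8 out of the DLT tabulation.

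**What to change.** In Sections 7.2.2.2 and 8.1, replace the reference to Cycle 1 with *during the DLT observation period as defined per cohort in Section 7.2.2.2*. Uncovered days in A7/A8 fall from 21 to 0, and A1 loses no protection.

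Keep the Section 7.4 ban on dose modification limited to Cycle 1. Extending it to Cycle 2 would conflict with delaying or withholding the Q3W dose for toxicity.

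For consistency, make the same replacement in the DLT summary in Section 10.3.1 and in the DLT-evaluable population in SAP 6.2.1.

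The cost is three wording changes in the protocol and one in the SAP, with no change to visits, samples or sample size. A patient who recovers from a Cycle 2 DLT would lose the option of continuing, as already happens for the same event in Cycle 1 or after day 42.
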